2.2.1 Secondary Objectives

1. To compare the proportion of patients with virological suppression at 24 months in patients receiving care via community ART models with those receiving care in the clinic (standard of care).

2. To compare Loss to Follow-up (LTFU) rates and missed dispensation of ARVs among individuals receiving care via community ART models with those receiving care in the clinic (standard of care), measured using routine health centre data

3. To compare HIV disease progression, and death among individuals receiving care via community ART models with those receiving care in the clinic (standard of care), measured using:

- CD4 cell count, WHO staging events, death from routine health centre data.

4. To qualitatively assess how health staff (including CHiPs) and PLWH on treatment experience the two models of care. This would be achieved through:

- Documenting treatment, adherence and retention experiences of PLWH accessing treatment through adherence club and home delivery models;

- Exploring the impact of the two models of care on access to treatment, adherence and retention according to the experience and perspectives of CHiPs and health facility staff;
- Qualitatively comparing how participant (PLWH and health staff) experience the models of care and experiences with the routine standard of care at the local health facilities;
- Qualitatively assessing participant (PLWH and health staff) perceptions about and experiences with the impact of the models of care on HIV services at the local health facilities.

5. To measure the health system costs of delivering the different community ART models.

In addition, we will measure the effect of the combined models on health facility crowding and waiting times as well as time to ART initiation of new patients in the 2 facilities (non- randomised comparison as both facilities have all models of care).

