3.0 Methods

3.1 Study Design and Setting

The study will be a cluster-randomized non-inferiority trial in a prospective cohort of adults enrolled in to ART care at two urban primary health care facilities that serve two of the HPTN 071 trial communities in Lusaka, Zambia. These two communities include Chipata and Kanyama, which are the Lusaka arms A and B communities of the parent trial (HPTN 071) respectively. The reason for conducting the study in these two communities is that they are located in an urban setting where there is a high number of HIV patients in care, thus overburdening the clinics and an ideal setting to determine if these community models of ART delivery benefit the health care system in urban Zambia by decongesting clinics and making treatment easier to access.

The HPTN 071 (PopART) trial is evaluating the impact of community level combination prevention package, which includes universal HIV testing, active linkage to care and intensified provision of ART, on population level HIV incidence. This is a three-arm cluster randomized trial being implemented in 21 communities of which 12 are in Zambia and 9 in South Africa. These interventions are being delivered by Community HIV Providers (CHiPs) who are members of the community, appointed to provide a package of basic services at household level particularly HIV counselling and testing, linkage to care for those who are HIV infected, HIV/TB education, adherence support, distribution of condoms, screening household members for TB and STI and linking household members for appropriate HIV prevention, treatment and care services.

Before the start of the main trial, mapping of the households and non-residential buildings, with a census to count the number of adults (≥ 16 years old) and children (≤ 16 years old) was done and the map of the communities was created based on global positioning system (GPS) coordinates of all households and non-residential buildings. Following the mapping the data was used to define the catchment area of the clinic and to divide it into “CHiP zones” with one CHiP team being responsible for a zone. Each zone within these communities has approximately 400-450 households served by the CHiPs. Table 2 shows the number of CHiPs teams/zones in the 2 communities with the population each CHiP teams covers and the number of HIV positive adults being cared for in each zone

Table 2: Total number of zones in the communities served by the CHiP teams

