4.0 Study Outcomes

The primary and secondary objectives for this study are listed in Section 2.2. The outcome measures for these objectives are listed below and will be measured in all study arms unless otherwise noted.

A. Primary Outcome – viral suppression at 12 months measured using the standard of care viral load testing equipment currently in place. Viral suppression will be defined according to National guidelines

B. Secondary Outcomes - these will include:

1. ***Viral suppression at 24 months*** – undetectable HIV viral load 24 months after entry into the models of care. This will be done as part of routine laboratory monitoring and measured using routine programmatic data.

2. ***Retention in care / Loss to Follow-up*** -Loss to follow-up from ART programmes describes all patients who are no longer in care and have an unknown outcome. A most useful definition of “loss to follow-up” should refer to patients with unknown outcomes(49). For this study, LTFU will be defined as “*no patient contact for 90 days or longer after the last given appointment*”.

Retention in care refers to *all patients retained in the HIV program*. Patients who are no longer retained in care with unknown outcomes will be classified as LTFU.

- In this study, retention will be defined as the number (%) of clients who are retained in the program at 6, 12 and 24 months after implementation of the intervention.
- The time to Lost to follow-up will be calculated in months according to the time interval between the dates of entry into the intervention to drop out, as recorded in the routine programmatic data.
- Proportion of patients that returned to mainstream care at 6, 12 and 24 months.

3. **HIV disease progression** – defined as having a new or recurrent WHO stage 3 or 4 condition after 6 months of ART, or a fall in CD4 count, (1). For patients with baseline CD4 count of < 200 cells/ μ l a fall of CD4 count to baseline or below after 6 months of ART; or persistent CD4 count < 100 cells/ μ l after 6 months of ART. (2). For patients with baseline CD4 count \geq 200 cells/ μ l, a persistent decline in CD4 count after two or more tests. For this study we will determine the following using routine health centre data:

- Proportion of patients who have had their CD4 count tests done at 6, 12 and 24 months after entering the models of care
- Proportion patients who developed a WHO stage 3 or 4 condition at 6, 12 and 24 months

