- Proportion of patients with CD4 count below 200 at 6, 12 and 24 months despite on treatment.

4. Death – defined as death at any point during the intervention due to any HIV related cause after enrolment into the study.

5. Participant choice of model and retention within that model. The following outcomes will be measured using programmatic and routine health centre data:

- Proportion of patients who enrolled into the models of care by sex
- Proportion (%) of eligible patients but refused to enter the model of care at baseline
- Proportion of patients who switched back to mainstream care at 6, 12 and 24 months and reasons for switching
- Number of club sessions and home visits that took place at 12 and 24 months after start of intervention

6. Drug Supplies –using routine health centre and programmatic data, we will determine:

- Number of groups/individuals missing at least one refill in the last 12 and 24 months (ART, Cotrimoxazole)
- Missed dispensations of ARVs at 6, 12 and 24 months.
- Proportion of pre-packed drugs returned to the clinic after a club session or home-based visit.
- Number of reported cases of ART drugs being pilfered after the start of the intervention.

7. Qualitative evaluation- of the acceptability and functioning of the two models of community ART delivery based on systematic structured observations of delivery, in-depth interviews and focus group discussions with key-informants (CHiPs, health facility staff) and longitudinal interviews with PLWH.

8. Economic Analysis – this will include:

- Measuring and comparing the incremental costs of the two intervention packages. The economic analysis will focus on measuring economic costs of the interventions from provider's perspective. The main focus will be on costs to the health services, including personnel, equipment and materials. The incremental cost of the interventions will be estimated by comparing costs of service provision and healthcare utilization with non-intervention healthcare facilities.
- Measure the impact of implementing the community ART delivery models on health systems and service delivery at local health centres in terms of technical and allocative efficiency of available HIV resource.

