This will be embedded in the community models of ART delivery to compare the incremental of delivering the two models. Patient specific resource utilization data will be collected prospectively alongside the main study. We will generate estimates of the costs to the health care system of providing the interventions, such as packaging of drugs for the models, stationary used and trainings. We will also consider recurrent costs for personnel (wages and related costs), laboratory tests, materials, equipment and supplies etc. Direct health benefits will also be measured by triangulating HIV disease progression and death data, and secondary data on quality of life and disability. Data sources will include case report forms and study records. Secondary sources such as peer reviewed publications and grey literature will be reviewed to complement primary data.

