The main focus of the economic analysis will be the cost of the models including equipment, materials, laboratory tests and personnel. Cost estimates will be collected for each of the resource items identified from the case report forms and study records. All cost data will be presented in Zambian Kwacha and in US\$. Data will be entered and cleaned in excel. Patient specific resource use data will be coupled with the unit cost estimates to generate a patient specific cost estimate. Mean patient costs will be calculated separately for study intervention arms and standard statistical analysis undertaken. Data analysis will be performed in both Microsoft (MS) excel and Stata-version 13.0.

A cohort model will be developed combining the costs and benefits from the intervention. This approach will provide a conservative estimate of the cost-effectiveness of the intervention, as it will only consider the direct health benefits of the trial participants and not account for the indirect health benefits (such as QALY gains or DALYs averted from the secondary infections avoided).

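### Each model's incremental cost is to be measured against facilities outside the trial, which confounds it with facility although a randomised control arm attends the same two clinics

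*Protocol*

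**What the plan says.** Section 4.0, item 8 states the comparator outright: the incremental cost of the models is to be estimated by "comparing costs of service provision and healthcare utilization with non-intervention healthcare facilities". The viewpoint is that of the health service: "The economic analysis will focus on measuring economic costs of the interventions from provider's perspective".

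The trial takes place in "a prospective cohort of adults enrolled in to ART care at two urban primary health care facilities" (Section 3.1). Section 2.2.1 plans a facility-level look at crowding, waiting times and time to ART initiation, and describes it as a "non- randomised comparison as both facilities have all models of care". That remark is not about costs, but it establishes that neither study clinic is free of the interventions.

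Section 3.1.4 allocates 35, 35 and 34 zones to Arms 1, 2 and 3. Arm 3 patients stay in clinic care. The Protocol Summary says that zones are randomised within each community.

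On cost data, Section 5.0 says: "Patient specific resource utilization data will be collected prospectively alongside the main study". Section 7.0 says: "Mean patient costs will be calculated separately for study intervention arms". The opening paragraph of Section 4.0 sets a default that outcome measures "will be measured in all study arms unless otherwise noted".

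**The concern.** The trial has a concurrent randomised control group at the two clinics where the models run, yet the stated cost comparator is a set of other facilities. In that comparison every intervention patient attends a study facility and every comparator patient attends some other facility. Intervention status and facility then coincide completely, and no number of extra patients or zones separates them.

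At stake is the figure for what clubs, or home delivery, add to or save from the cost of standard care. Section 1.2 promises policy makers evidence on cost-effectiveness, and Section 7.0 plans a cohort model that combines costs and benefits. If the outside contrast supplied the costs for that model while Arm 3 supplied the effects, the two would refer to different populations.

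**Working it through.** The Protocol gives no cost, no cost variance, no number of outside facilities and no costing sample size. There is therefore no planned figure to reproduce, and the check is structural.

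**1. Where the comparator lies.** Study facilities: 2 (Section 3.1). Facilities running all models: 2 (Section 2.2.1). Non-intervention facilities inside the trial: 2 − 2 = 0. Read as written, the comparator is outside.

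**2. Whether another section restores Arm 3.**
- The default in Section 4.0 may bring Arm 3 costs into the data. It does not make Arm 3 the comparator, because item 8 names a different one.
- The economic paragraph of Section 5.0 speaks of comparing the two models.
- Section 7.0 names the intervention arms for mean patient costs and is silent on Arm 3. Its opening sentence does compare each intervention arm with control, but in connection with the viral endpoint.

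So no section does.

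**3. What each contrast estimates.** Write the mean cost of standard care at a facility as μ + F, where F is the facility's own deviation. Let d be the full effect of a model on its patients' cost, and s any change in Arm 3 costs caused by the models running in the same clinic.
- Model against outside facilities: d + (mean F of study facilities − mean F of outside facilities).
- Model against Arm 3, within community: d − s. The F terms cancel.
- Clubs against home delivery, both measured against the same outside mean X: (C1 − X) − (C2 − X) = C1 − C2. The outside comparator drops out and the contrast remains randomised.

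Cancellation in the second line is exact if the contrast is taken within community. Pooled without stratification, the first community's share of zones is 18/35 = 0.514 in Arm 1 and 18/34 = 0.529 in Arm 3, so with equal zone sizes only about 0.015 of the difference between the two clinics would remain.

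**4. How large the facility term could be (illustration only).** If facility mean costs vary with coefficient of variation CV, the standard error that facilities alone contribute to a contrast of 2 study facilities with m outside ones is CV × √(1/2 + 1/m), as a share of mean cost. Both CV and m are assumptions.

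| Assumed CV | m = 2 | m = 10 |
|---|---|---|
| 0.1 | 10.0% | 7.7% |
| 0.2 | 20.0% | 15.5% |
| 0.3 | 30.0% | 23.2% |
| 0.4 | 40.0% | 31.0% |

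For example, with m = 10, √(0.5 + 0.1) = 0.775, and 0.2 × 0.775 = 15.5%. Even with unlimited outside facilities the factor falls only to √0.5 = 0.707, because there are still just two study clinics. In the within-community contrast with Arm 3 this term is zero.

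**The case against.** The best defence is spillover. The costing takes the provider's view, and Section 3.1 gives decongestion of the clinics as a reason for the study. Arm 3 patients use those same clinics, so shared staff time and overhead may alter their costs too: the term s above is not zero. A contrast with Arm 3 would then miss savings that all arms share, and a facility untouched by the models has something to offer. This stands as a real limit of Arm 3. It supports an outside comparison beside the randomised one, but not in its place. Item 8 gives no such reason, and it does not label its comparison non-randomised as Section 2.2.1 does for crowding and waiting times.

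A second defence is that the phrase may be loose wording for clinic-based care in Arm 3. That is possible. The text would then misdescribe the comparator, and the same edit is needed.

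A third is that the number and selection of facilities, and any adjustment, may belong in a plan that is not shown. That is fair, and their absence is not the complaint. The point concerns the comparator that the Protocol does state.

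Some stronger readings are tempting but not supported:
- *That Arm 3 costs are thrown away.* Nothing says so. The default in Section 4.0 covers all arms, Section 5.0 does not exclude Arm 3, and Section 7.0 merely omits it.
- *That secondary objective 5 depends on this contrast.* It asks only for the health-system costs of delivering the models, which needs no standard-of-care comparator.
- *That the cohort model is bound to use the outside contrast.* Section 7.0 does not say which cost difference enters it.

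**Conclusion.** The concern holds for one quantity: the incremental cost of each model relative to standard of care. As item 8 is written, that quantity is confounded with facility, while a randomised comparator (34 zones against 35 in each intervention arm) exists at the same two clinics.

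A reader might infer that the whole economic comparison is biased, or that a bias of 10% to 40% has been shown. Neither follows. The club-versus-home cost contrast is unaffected, and the primary non-inferiority result is untouched. The percentages above are spreads under assumed inputs. The documents allow neither the direction nor the size of the actual bias to be derived.

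The conclusion rests on reading non-intervention facilities literally, which Sections 2.2.1 and 3.1 together place outside the trial. It is worth correcting because the result is meant to inform policy, but it concerns part of a secondary outcome.

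**What to change.** In Section 4.0, item 8, define incremental cost as mean patient cost in Arm 1 minus that in Arm 3, and in Arm 2 minus that in Arm 3. Analyse by allocated zone, allow for zone clustering, and stratify by community as the randomisation does.

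In Section 7.0, extend the sentence that now reads "Mean patient costs will be calculated separately for study intervention arms" so that it covers all three study arms. In Section 5.0, confirm that resource-use collection includes Arm 3 patients.

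Keep any comparison with outside facilities as a supplementary analysis. Label it non-randomised and give its purpose as examining spillover into Arm 3 through decongestion and shared overhead.

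The cost is mostly wording, plus resource-use data on Arm 3 patients at the two study clinics if these are not already planned. This should be settled before collection begins, since missed data may be hard to recover. The remaining drawback is that the Arm 3 contrast may not capture system-level savings common to all arms, which is why the supplementary analysis is worth keeping.

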5.0 Data Collection and Tools

Data will be collected at the following points:

Baseline

Three (3) months

Six (6) months

Twelve (12) months

Twenty four (24) months

Routine data will be collected using the national HMIS system and patient clinic records. At baseline, the following variables will be collected from patients to determine their influence on the outcomes:

- Age, sex, weight
- Recent CD4 count before enrolling into the models of care
- Viral load
- WHO stage at enrolment
- Date of starting ART
- Current drug regimen.

To maximize the validity of this information, the study team will work closely with the health centres to improve the collection and management of these routine data.

Data captured from the community models of ART delivery will be collected using the same hand held collection device being used in the main HPTN trial. A specific programme for this model will be installed in the device. This program is designed to maximize the quality of data collection using drop down lists and incorporating checks to avoid simple data entry errors. The CHiPs will undergo formal training on how to use the software to capture data at community level and sync it with the facility database and this training will be documented and retained in the site files.

Under the leadership of the Zambian Ministry of Health, the community ART steering committee has agreed upon a set of core indicators to be used to monitor and evaluate the community ART service delivery models being piloted by different partners. To facilitate the collection of the key indicators across both models, a list of common indicators will be used and this will be captured from both smart care and routine programmatic data.

Appendix 2 gives a detailed description of the data captured by the Chips in both Adherence clubs and home-based visits. The EDC program will capture data as required by the National ART community module for stable on care patients which has been developed by EGPAF and implementing partners. The following data will be captured in the device during the community ART model visits:

At clinic level:

- Patient ART registration details- Name, Sex, Age, ART number

At community Level (Adherence Clubs and Home based Visits)

- Date of visit
- Symptom Screen (fever, weight loss, cough, headache)
- Pregnancy screening for females
- Adherence counselling and types of counselling
- Pre-packed drugs dispensed
- Services referred for PMTCT, ART, STI, VMMC, etc.
- Next community and clinic visit appointment

Data captured electronically during community visits will be linked to the HIV care databases at the health centre. The study team will work closely with the Ministry of Health and implementing partners

supporting the sites to collect relevant data from both the supply and demand side. Data that will be captured electronically during the club and home visits will be synced at the end of the day with the health care centre database. This is to ensure that indicators used for routine monitoring and follow-up will be entered in the current smart care system at facility level. The table below summarizes the core indicators that will be collected at both facility and community levels for the purpose of monitoring and evaluation.

Table 6: Common indicators for community ART models

Common Indicators for Community ART Models of Care		
Main	Core Indicator	Data Source
1. Recruitment	Proportion of patients enrolled into Home-Based ART models by sex	Smart care / HMIS
	Proportion eligible but refused	Consenting register
	Proportion of patients dropping out (within 1,3,6 and 12 months)	Routine data/ Programmatic data
	CD4 count at enrolment	Smart care
	Time on ART before enrolment	Smart care
2. Retention	Number (%) of clients retained at 1,3,6,12 and 24 months	Smart care
	Loss to follow up by reason:	Smart care
	
 • Dead • Transfer • Lost 	
	Number of patients returned to mainstream care (@ 3, 6, 12, 24 months)	Smart care
3. Laboratory	% of clients who developed an OI @ 3, 6, 12 and 24 months	Smart care and routine programmatic data
	Proportion of patients who have had viral loads within the last 6 months	Smart care and routine programmatic data
	Proportion of patients who have had CD4 count in the last 6 months	Smart care and routine programmatic data
	Proportion of patients with viral suppression at 12 and 24months	Smart care and routine programmatic data
4. Drug Supplies	Proportion of patients with CD4 count below 500 in the last 12 months despite treatment	Smart care and routine programmatic data
	Number of individuals missing at least one refill in the last 6 and 12 months	Smart care and routine programmatic data

Additional data collected for measuring the outcomes of the study objectives will be collected from patient clinical records. The key clinical indicators will be collected from smart care and HMIS and these includes:

- Proportion of patients with continuous immunologic/virologic suppression
- Proportion of patients who develop opportunistic infections in the models of care
- Transition rates of newly eligible patients into the community models
- Transition rates of patients from community models back to facility care

Data Security

Data will be securely stored according to Ministry of Health and Smart Care guidelines that are already in place for all health care centres providing HIV care. All CHiPs involved in community of ART model delivery will have to sign a consent form as per smart care National Guidelines which explicitly explains data confidentiality and respect of clients. Data captured electronically in the device is encrypted and once it is synced with the health centre database, protected by Microsoft SQL security. Access of all data in the health centre database will be based on user right and every user in the facility has to agree to terms of use, which is currently in place. The Audit Trail in Smart Care that is currently in place in all ART health centres logs key events, which occur in the system. It logs information such as who logged into the system, which patient reports they run, changes to inventory and who created a back up. Every single interaction has the identifier of whoever entered the data as well. This trail will be used for security and audit purposes.

In order to obtain the data for monitoring and evaluation as well as for research purposes both by implementing partners and Zambart research teams, permission will be sought from the Ministry of Health. The study team will then periodically extract this data for measuring the outcomes of the study.

Investigators will also allow inspection of all study-related documentation by authorized representatives of the HPTN LOC, SDMC, LC, NIAID, US and in-country government and regulatory authorities and IRBs/ECs. A site visit log will also be maintained at the study site to document all visits.

Qualitative Data Collection

Participants will include CHiPs and health facility staff involved in the models of care and based at the two urban health facilities and PLWH will be selected based on their qualitative representation of particular gender, age, experience and (for PLWH) household groups. Participant numbers will be relatively small. We estimate that participants will include approximately four CHiPs and four health facility staff in each of the two sites and 12 PLWH in each of the two sites.

Semi-structured key informant in-depth interviews (IDI) with health facility staff and CHiPs will be conducted at the two facilities. In addition, one focus group discussion in each site with CHiPs will also be conducted. These two data collections activities (FGDs and IDIs) will only be conducted once after one year and six months into the intervention.

For PLWH, data will be collected through focus group discussions (FGD) as well as in-depth interviews (IDI) for those that will not be comfortable with participating in FGDs. These activities will also be conducted once after one year and six months into the intervention. Moreover, Structured observations of the two delivery models and routine care will be carried out intermittently (Quarterly from the start) by Zambart social scientists in the two mentioned sites.

In addition, other existing social science data collected as a component of the wider PopART trial will be reviewed to help develop the research tools to be used (IDIs, structured observations and FGDs) and for comparative interpretation. For example, drawing on data on PLWH involved in other longitudinal enquiry in other PopART communities who are continuing to go to the health facility for care.

Key themes would include: the impact of the models of care on livelihood options, HIV related stigma and social relations; satisfaction with the modes of delivery; and comparison with routine ART delivery at the public health facility.

The data from this study will be transcribed, coded and managed using ATLAS ti and analysed using key themes and interdisciplinary discussion about key outcomes.

Economic Analysis

This will be embedded in the community models of ART delivery to compare the incremental of delivering the two models. Patient specific resource utilization data will be collected prospectively alongside the main study. We will generate estimates of the costs to the health care system of providing the interventions, such as packaging of drugs for the models, stationary used and trainings. We will also consider recurrent costs for personnel (wages and related costs), laboratory tests, materials, equipment and supplies etc. Direct health benefits will also be measured by triangulating HIV disease progression and death data, and secondary data on quality of life and disability. Data sources will include case report forms and study records. Secondary sources such as peer reviewed publications and grey literature will be reviewed to complement primary data.

